Title: Prognosis and therapeutic biomarkers for glioblastoma patients (for research only)

Investigators: Principal Investigator, other co-investigators

PI: [name]

Co-PI: [name]

1. Introduction/Background

The purpose of this study is to investigate if the potential biomarkers identified could be used for facilitating the diagnosis and prognosis of patients with glioblastoma (GBM).

GBM, accounting for 50% of central nerve system (CNS) tumors, is a deadly disease with no effective curable therapy. To improve the quality of patients' life and enhance the therapy response, Optune was developed and approved by the US Food and Drug Administration (FDA) for treating recurrent GBM (1-9). Now both Optune and Adjuvant TMZ plus Optune treatment are considered as a standard strategy for maintenance therapy to extend patients' life after surgery and chemotherapy (2, 6). Currently, diagnosis and prognosis of GBM rely on magnetic resonance imaging (MRI), computed tomography (CT), and biopsy (10). These diagnosis and prognosis processes for patients with GBM are expensive, difficult, and inaccurate. Biopsy of brain tissues from GBM patients is a very aggressive procedure, and it is extremely difficult to re-biopsy. By analyzing previously published data derived from microarray and next generation sequencing as well as the experimental data generated from our lab, we have identified a group of genes that have potential to be used as biomarkers for GBM prognosis.

To ascertain if the potential biomarkers could be used to facilitate the diagnosis of patients with GBM, the goal of this proposed study is to determine the expression levels of selected biomarkers in GBM tissues and the cerebrospinal fluid (CSF) from patients with GBM receiving different types of treatment against controls.

[figure not shown]
2. Significance

There is no effective therapy for GBM. There is a critical need for early diagnostic and prognostic biomarkers for GBM. The completion of this study will provide a potential biomarker for diagnosis and prognosis of GBM patients.

3. Objectives & Specific Aims

The **objective** of this proposed study is to determine the expression levels of a panel of markers including CD133, CD44, ABCC3, TNFRSF1A, AKT1, IDH2, and MGMT in GBM tissues and the CSF, blood, and saliva from patients with GBM receiving different types of treatment as described in Figure 1 and the non-brain tumor patients (controls). Our aims are: 1) To compare the differences of CD44 between the control group and the combined cancer groups at baseline; and 2) To compare the levels of CD44 and other markers among the 3 different groups such as control vs. GBM patients and Optune vs. Optune + TMZ after 8 weeks of treatment. Exploratory analysis of all other markers will be performed.

Figure 1 Overall strategy

4. Methodology

4.1 Study Design.

To reach our goal, a small clinical study will be performed with the support from NovoCure Inc. In this study, 30 participants will be enrolled in which 10 non-brain tumor patients (e.g., patients will have other types of minor neurological disorder(s) that necessitate a lumbar puncture e.g., headache, epilepsy or neurodegenerative disorders such as Alzheimer's disease or Multiple sclerosis or Parkinson's disease) will be used as the control. As shown in Figure 1, 20 patients (n=20) with GBM will be divided into two groups; patients in group 3 will receive the combination of TMZ (150-200 mg/m² orally every day; 5 consecutive days per 28-day treatment cycle for 6 cycles) with Optune and patients in group 2 will receive Optune only. (The GBM patients will be monitored for tumor size using MRI and CT scan before and after each type of treatment, which is standard of care for all GBM patients.) We will collect the CSF (5 ml), blood (2 ml), and saliva (5 ml) from each participant as indicated in Figure 2 before and after treatment (Optune alone or Optune plus TMZ for detection of biomarkers. These samples will be used for detection of selected biomarkers at gene (RNA and DNA) and protein levels. CSF is standard of care for all GBM patients, we will ask to store the leftover tumor tissues for our research.

4.2 Subject Selection/Participants.

The participants in both non-brain tumor group and GBM groups (male and/or female, there is no preference at this time) should be over 22 years old without pregnancy, or an infectious disease (cold, flu, HIV, etc.) or a blood disorder (e.g., lack of platelets, anemia, thrombosis) or vascular malformations. For controls, only patients evaluated for the neurological disorders whose evaluation required spinal taps at both the Neurology clinic and the Brain Tumor clinics will be used for this study. This is an exploratory pilot study. Based on others previous experiences, 30 subjects (10 subjects in each group) will allow us to estimate the levels of selected biomarkers in the body fluids of different groups of patients and the potential value of these selected biomarkers for GBM prognosis.

4.3 Procedures/Methods.

For the non-brain tumor control group, 5 ml of CSF, 2 ml of blood, and 5 ml of saliva will be collected one time from each participant. For the GBM patients, patients will first receive surgery to remove the tumor (the tissue will be used for diagnosis and we will use the left over for the biomarker detection) followed by radiation and/or chemotherapy according to patients' health conditions. (CSF are standard of care for these patients.) Thereafter, the physician will discuss with the patients and help patients pick their FDA approved treatment options to receive Optune or Optune plus TMZ.

All of the GBM patients will be asked for blood, saliva, and CSF withdraws at three time points as indicated in Figure 2 (the first time point is at after surgery +/- 1 week and before the combination of radiation and chemotherapy; the second time point is immediately before starting Optune/TMZ treatment +/- 3 days [at 6 weeks after the combination treatment]; and the third time point is at 8 months after the Optune/TMZ treatment +/- 1 month). The samples collected will be used to determine the levels of selected potential biomarkers at protein, DNA/RNA levels. These data will be used to assess the efficacy of the treatments for GBM patients and the correlation of the efficacies of the treatments with the expression levels of testing biomarkers in their CSF, blood, and saliva.

Method for saliva collection: Patients should be consented on day one and come back for blood and saliva withdrawal. For saliva collection, participants will be instructed to fast overnight before saliva collection. Teeth brushing should occur at least one hour prior to saliva collection. Saliva collection should (ideally) occur between 8:00 am and 10:00 am. Upon arrival at the clinic, patients should be instructed to rinse mouth with deionized (DI) water for thirty seconds (30 s) to remove any residual foreign particles (e.g., food) and/or mucus from the mouth prior to saliva collection. Water used to rinse mouth can be spit out and discarded. Wait one minute after rinsing mouth before beginning saliva collection. Saliva will be collected from both "normal patients" and "patients with the disease" using the passive drool method (i.e.,

non-chemically stimulated, whole saliva collection), as previously described. Patients should be informed that we strictly want to collect saliva, mucous and/or phlegm should not be collected. After the one minute waiting period, start a timer and instruct patients to think about eating their favorite food while making a chewing motion with their jaw (these actions help stimulate saliva production). Patients should pool saliva under their tongue and passively “drool” saliva through a drinking straw (cut to a length of approximately 2 inches (11) into a 15 mL centrifuge tube. Please keep collection tube in a cup filled with ice (crushed ice is preferable) during saliva collection to help preserve biomolecules. Final volume of saliva collected should be ~ 5 mL (no less than 3 mL). Upon completion of saliva collection, stop timer and record total time taken to collect the sample (this time will be used to estimate saliva production rates). Immediately after saliva collection, transfer 15 mL centrifuge tube to a -80 °C freezer for storage. Patients may resume a normal eating schedule immediately after completion of saliva collection.

Subject recruitment & enrollment plan

For GBM patients, there are over 60 GBM patients enrolled at Baylor Scott & White Health each year. The coordinators will screen patients' files to find potential participants of patients with GBM. The patients are at least 22 years old and without pregnancy, or an infectious disease (cold, flu, HIV, etc.) or a blood disorder (e.g., lack of platelets, anemia, thrombosis) or vascular malformations will be selected and interviewed for participating this study after discussing treatment options with their physicians.

For the participants in the control group, there are several hundreds of patients with neurological disease (e.g., patients with Alzheimer's or multiple sclerosis or Parkinson's disease) enrolled at Baylor Scott & White Health yearly. CSF and blood draws are required for diagnosis of these patients. As CSF draw is standard of care, we will be able to find those individuals from enrolled patients who have other neurological disorders such as Alzheimer's or multiple sclerosis and use the leftover CSF for our research. Thus, there is no need for advertisement. The coordinators will screen patients' files to find potential participants of patients with non-brain tumor and then the coordinators will interview those individuals and recruit them for this study. As soon as the project is approved by the IRB committee, we will start to recruit patients for this study.

Although there is little risk for patients who participant in this study, we still ask all participants to sign an Informed Consent form. All participants will be given an IRB approved Informed Consent form by their doctors before they enter in this study.

Incentives for participation/compensation

The participants will be paid for giving their blood and CSF for the tests (\$25 each time per test) after each visit. The payment will be made by from Baylor Scott & White Research Institute and it is considered taxable income. The participants must be eligible to be paid in the United States and willing to complete all the necessary tax/legal paperwork to receive this payment.

Study procedures for individual visits/interventions and/or interactions

Optune, a Novo treating tumor field (NovoTTF) device, is approved by FDA for treating patients with relapsed GBM. Recent studies indicate that it is possible for people with newly diagnosed GBM living longer when Optune is used together with the chemotherapy TMZ.

The control group will have no interaction with anything as they will not receive any anticancer treatment and all participants without brain tumor will be signed up in this group.

Data collection variables

The time points for data and sample collection will follow the schedule as indicated in Figure 2. The first point will be served as the baseline; the second point will be the intermediate; and the third point will be the endpoint for the biomarker study of using CSF samples. The data generated from the patients' samples will be kept in the lab. As these data do not contain any privacy information, there will be no privacy concern.

The data for the tumor sizes and patients' general performs will be a part of the standard care. Data collection forms can be Excel spreadsheets or created in Microsoft Access (the Data Management group can create these for the PI).

For privacy concerns, all the information about participants from this study will only be shown to the people working on the study. The results of this study may be published in a scientific book or journal. If this is done, the name of any participants will not be used. All information about participants from this research project will be kept in a locked office. Information that is kept on computers will be kept safe from access by people who should not see it. Sensitive information is not allowed to transfer or distribute to the third party without permission. All investigators who deal with collected tissue samples on this application have taken or will take the respective institutional "human subject protection" training for this project. Only Key Study Personnel (KSP) will have access to collected data and that it will be housed in secure environment. The data will not be destroyed at least for 6 year.

Tumor tissues will be collected from patients for diagnosis and future research e.g., evaluating the levels of biomarkers selected. The tissues will be snap-frozen (fresh-frozen, FF) and then stored at -80 or liquid nitrogen. Alternatively, it could be formalin-fixed paraffin-embedded (FFPE) for long time storage (10 years). All samples are expected to be used for diagnosis, thus, though the original samples may be labeled with patients' information. However, the patients' information will not be released to the researchers. The pathologist will change the label to GBM with numbers only.

The 5 ml of CSF collected from each patient each time will be centrifuged at 3500 rpm at 4°C for 10 min to remove any possible blood contamination and kept in the dry ice or stored at -80°C immediately. The samples will be used for determining the protein levels of selected potential markers. All the samples will be labeled with number system without PHI information and the samples are expected to be analyzed within 12 months. The amount of samples collected in this study is very limited and we do not expect any sample left after the study.

For the privacy concerns, only publishable data will be shared by the third party. All samples will not be transferred from Baylor Scott & White Health to a non -Scott & White Health laboratory for analysis. In case, there is a need to transfer the materials from Baylor Scott & White Health to a third party for sample analysis, permission. A Materials Transfer Agreement (MTA) or Data Use Agreement (DUA) will be required before any materials or data can be shared. Medical Research Building (MRB), an MTA is also required. The Office of Research Business Development can assist with development of these documents

Subject withdrawal

The patients have the right to leave the study anytime. The data collected will be used for the analysis as long as the data are meaningful. Otherwise, more patients will be enrolled.

Reporting adverse events or other significant events

As both Optune and TMZ are FDA approved treatment options for GBM patients, there are no significant adverse events caused by these treatment. In an unlikely case, there are any significant events; it should be reported to IRB immediately.

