4.3 Power Calculation

The goal of the study is to compare the differences in the CSF, blood and saliva levels of CD44 between 1) the control group and the Optune alone and the TMZ + Optune group; and 2) Optune alone vs, TMZ + Optune alone.

There is no previous literature on CD44 levels in GBM. To calculate a sample size, we are assuming that the baseline and post treatment levels of CD44 standard form in the CSF will be approximately 327 ± 134 ng/ml and 185 ± 103 , respectively, similar to those reported by Kawano et al. for head and neck cancer(12). One of the drawbacks of the report is that they only reported the median and do not specify if it is the standard deviation or range that they reported.

For the primary goal, it is assumed that the median is similar to the mean and the reported value is the standard deviation. Further assumptions are: sample sizes of n=10 and n=20 (for the control and the cancer groups, respectively); significance level of 0.05; expected means of 327 and 185 (for the cancer and the control groups, respectively); common standard deviation of 115; independence of the sample units and normality of the observations. The power was calculated using a two sample t-test and it was found to be 87%. Power calculation was performed with PASS v.13.0.4.

4.4 Data Analysis.

Descriptive statistics will be provided. Categorical data will be reported as count (percentages). Continuous data will be reported as mean (standard deviation) or median (range) as appropriate. A two sample t-test will be used to compare the biomarker level between groups, unless the distributions are found to be non-symmetric. In that case, Wilcoxon-Rank-Sum tests will be used.

5. Human Subjects

Thirty individuals will take part in this study at Baylor Scott & White Healthcare. Body fluids we requested are considered to have concern of human subject.

Risks (including physical, emotional, social, and/or privacy)

Risks of Radiation – Diagnostic Test: Patients will have the same amount of radiation exposure regardless of whether the participant elects to take part in this research study or receives standard medical care.

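### Aim 1's baseline GBM fluid sample is taken after tumour surgery, so the comparison with controls cannot by itself support the protocol's statements about diagnosis

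*Protocol*

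**What the plan says.** Three statements in the protocol together fix the timing of the primary comparison.

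- Section 3 (Objectives & Specific Aims) gives Aim 1: "To compare the differences of CD44 between the control group and the combined cancer groups at baseline".
- The part headed Data collection variables defines the term: "The first point will be served as the baseline; the second point will be the intermediate".
- Section 4.3 (Procedures/Methods) says that GBM "patients will first receive surgery to remove the tumor", and places the first draw thus: "the first time point is at after surgery +/- 1 week and before the combination of radiation and chemotherapy". The second draw comes just ahead of Optune/TMZ and the third about 8 months later.

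Controls give CSF, blood and saliva once. Section 4.3 (Power Calculation) sets the comparison in those fluids; its goal is to "compare the differences in the CSF, blood and saliva levels of CD44 between" the groups.

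On purpose, section 1 names diagnosis alongside prognosis, and section 2 says: "The completion of this study will provide a potential biomarker for diagnosis and prognosis of GBM patients".

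**The concern.** A marker meant to help diagnose GBM has to be seen in patients who still have the tumour. Here the sample called baseline is a baseline only with respect to chemoradiation and Optune/TMZ. It is not a baseline with respect to surgery.

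The two arms of Aim 1 then differ in more than having GBM. One arm has just had an operation to remove its tumour. The other, as described, has had no tumour surgery. If CD44 differs, part of the difference may come from the operation. If it does not, the reason may be that the tumour has been taken out. Neither result says what fluid CD44 looks like with the unresected tumour in place. What is at stake is the conclusion that may be drawn from the primary comparison, and in particular whether it can be reported as evidence on diagnosis.

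The wording of the window adds a smaller problem. A tolerance of plus or minus one week attached to surgery could, if applied literally, let pre-operative draws into a sample defined as post-operative.

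**Working it through.** **Step 1: sequence of events for GBM patients** (section 4.3 Procedures/Methods, with labels from Data collection variables).

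| Order | Event | Fluid draw? | Label |
|---|---|---|---|
| 1 | Surgery to remove the tumour | none targeted before it; leftover tissue kept | – |
| 2 | After surgery, before chemoradiation | yes, first point | baseline |
| 3 | Before Optune/TMZ, 6 weeks after chemoradiation | yes, second point | intermediate |
| 4 | 8 months after Optune/TMZ | yes, third point | endpoint |

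Aim 1 uses the first point. None of the three listed points is targeted before surgery.

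**Step 2: does the tumour tissue fill the gap?** No. It is the only material that represents the tumour before removal, but controls supply fluids only. Tissue therefore has no counterpart in the control group, and the power section sets the comparison in fluids.

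**Step 3: the window.** If surgery is day 0, a literal plus or minus one week runs from day −7 to day +7, and half of it lies before surgery. The stated target is nevertheless after surgery, and surgery is said to come first. The protocol also uses the same plus-or-minus notation as a visit tolerance at the other two points. A tolerance around a post-operative visit is therefore the more natural reading. Figure 2, to which the text refers, is not available here and may settle it.

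**Step 4: the power figure.** Inputs from section 4.3 (Power Calculation): means 327 (GBM) and 185 (control), common SD 115, n = 20 and 10, significance level 0.05. Two-sided testing is assumed because the section does not state sidedness.

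- Difference: 327 − 185 = 142 ng/ml.
- Standard error: 115 × √(1/10 + 1/20) = 115 × 0.3873 = 44.54.
- Noncentrality: 142 / 44.54 = 3.19, with 10 + 20 − 2 = 28 degrees of freedom.
- Power from the noncentral t distribution: 86.8%, which matches the stated 87%.

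**Step 5: context only.** With the same n and SD, power is 97.0% if the true difference is 25% larger (177.5 ng/ml), 63.6% if 25% smaller (106.5) and 33.7% if halved (71). Power of 80% needs about 129 ng/ml. These multipliers are assumptions. The documents give no post-resection CD44 value, so the range shows how sensitive the calculation is and does not correct it.

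**The case against.** Much can be said for the protocol.

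- *Emphasis.* The title speaks of prognosis and therapeutic biomarkers, section 4.2 calls the study an exploratory pilot and refers to prognosis, and Aim 1 itself does not mention diagnosis. The section 1 goal covers tissue as well as CSF and openly describes treated patients, and section 2 speaks only of a potential biomarker. This stands, and it lowers the weight of the point. It does not remove it: sections 1 and 2 still name diagnosis as a purpose and as something that completion of the study will deliver, without saying that the fluid comparison is post-operative.
- *Coherence of the baseline.* The surgical tissue is used for diagnosis, and a baseline ahead of Optune/TMZ is sensible for following treatment. That is fair, and it is why no pre-operative draw is asked for.
- *Incomplete resection.* The documents do not say that resection is complete, so the sample may reflect residual tumour. This stands too. The limit therefore applies only to the fluid level with the unresected tumour in place, and the sample may still say something about GBM.

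Two stronger readings are tempting and are not supported. A reader might infer that the trial is underpowered because resection lowers CD44. The documents give neither the direction nor the size of any such change, and the 87% is arithmetically right. Section 4.3 (Power Calculation) also says openly that "There is no previous literature on CD44 levels in GBM" and that its means are borrowed from head and neck cancer. A reader might also infer that the baseline will in fact mix pre- and post-operative draws. Only a literal reading of the window allows that, and it is the less natural one.

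**Conclusion.** The point holds as a limit on what Aim 1 can conclude. On the text, its baseline contrast is post-resection GBM (n=20) versus controls without described tumour surgery (n=10). By itself it cannot support a statement about diagnosing GBM with the tumour in place.

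No numerical bias can be attached, because the effect of resection on CD44 is not documented. No power shortfall is shown, and the sensitivity range is not part of the finding. The window wording is a secondary ambiguity that is easily removed.

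The conclusion rests on the written time points being complete; Figure 2 could not be checked. Severity is minor, since this is an exploratory pilot and the remedy is wording.

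**What to change.** 1. Restate Aim 1 and its planned conclusion as *post-resection GBM versus control*. In sections 1 and 2, limit the diagnostic statements so that no claim about diagnosing GBM with the tumour in place is drawn from Aim 1.
2. Reword the first sampling window in section 4.3 (Procedures/Methods) as strictly after surgery and before chemoradiation, and keep a stated upper time limit. Without the lower bound, draws could fall on both sides of surgery. Without the upper limit, they could spread over the whole interval before chemoradiation, which would add variation in time since surgery.

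The cost is a narrower diagnostic claim. The number of draws, patients and tests does not change. The fix does not supply evidence from unresected patients; it only stops Aim 1 from being read as if it did. Adding the power range to the power section is optional.

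### Does the ±3 days on the second GBM sample let an on-treatment draw count as the pre-treatment one?

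*Protocol*

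**What the plan says.** Section 4.3 (Procedures/Methods) sets three sampling times for GBM patients in a single sentence:

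- Sample 1: "the first time point is at after surgery +/- 1 week and before the combination of radiation and chemotherapy".
- Sample 2: "the second time point is immediately before starting Optune/TMZ treatment +/- 3 days [at 6 weeks after the combination treatment".
- Sample 3: "the third time point is at 8 months after the Optune/TMZ treatment +/- 1 month".

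The sentence refers to Figure 2 for the schedule; that figure is not reproduced in the text available here. Section 4.1 gives the purpose of the sampling as collection "before and after treatment (Optune alone or Optune plus TMZ for detection of biomarkers". It also separates the two treated groups: one takes TMZ with Optune, while "patients in group 2 will receive Optune only". The section on data collection variables names sample 1 the baseline, sample 2 the intermediate point and sample 3 the endpoint. Section 4.3 adds a general statement of use: "These data will be used to assess the efficacy of the treatments for GBM patients".

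**The concern.** Sample 2 has two reference times, the start of Optune/TMZ and a point six weeks after the combined radiation and chemotherapy, but only one tolerance. In samples 1 and 3 the tolerance comes after the time it qualifies. By the same pattern, sample 2's tolerance would attach to treatment start. A coordinator could then regard a draw two days into treatment as in window, although the same phrase calls it a draw before treatment.

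Sample 2 is the only draw placed directly before Optune/TMZ, so it is the natural reference for a change over that treatment. A late draw would be an on-treatment value labelled as a pre-treatment one. The exposure would also differ by group, with Optune in both but TMZ in group 3 only. Up to 20 draws (10 per group) fall under this wording, and a CSF sample cannot be retaken as a pre-treatment sample once treatment has begun. The tolerance could be used in practice, because collection is a scheduled visit: "Patients should be consented on day one and come back for blood and saliva withdrawal".

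**Working it through.** **1. The plan's own figure.** Section 4.3 (Power Calculation) gives n = 10 controls and n = 20 cancer patients, means 185 and 327, common SD 115 and significance level 0.05. The difference is 327 − 185 = 142. The noncentrality is 142 / (115 × √(1/10 + 1/20)) = 3.188 on 28 degrees of freedom. The two-sided t-test power is 86.8%, which agrees with the stated 87%. This figure concerns control against combined cancer groups. Aim 1 makes that comparison at baseline, which is sample 1, so sample 2 does not enter it.

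**2. Days accepted under each reading.**

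- Tolerance on treatment start (day 0): days −3 to +3, seven calendar days, of which +1, +2 and +3 fall after the start day.
- Tolerance on the six-week point: 42 − 3 = 39 to 42 + 3 = 45 days after the combined treatment.

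The requirement that the draw precede the start is written into the sentence under both readings and must be applied evenly:

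| Reference time | Order respected | Order ignored |
|---|---|---|
| Treatment start | 0 late days | 3 of 7 late days |
| Six-week point | 0 late days | depends on the start; 3 of 7 (days 43–45) if treatment starts on day 42 |

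So the choice of reference time does not create the problem. A late draw arises only if the order is set aside, and then it can arise under either reading.

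**3. What word order shows.** In sample 3 the tolerance follows the mention of Optune/TMZ treatment but qualifies the numerical interval of 8 months. In sample 2 the only numerical interval is the 6 weeks. The pattern therefore does not settle the matter for treatment start. Sample 1 has the same looseness, a two-sided week around a draw that must follow surgery, and it is unlikely to mislead. Recruitment describes patients as "interviewed for participating this study after discussing treatment options with their physicians", and section 4.3 places surgery before the choice of Optune or Optune plus TMZ.

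**4. Size if a draw were late.** Assume CD44 moves linearly from 327 to 185 ng/ml after treatment start. The protocol gives two durations: 8 weeks (Aim 2, section 3) and 8 months (section 4.3).

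- Over 8 weeks: 142 × 3/56 = 7.6 ng/ml, and 7.6/115 = 0.07 SD.
- Over 8 months (243.5 days): 142 × 3/243.5 = 1.7 ng/ml, and 1.7/115 = 0.02 SD.
- Effect of one late sample on a group mean of 10: 0.76 or 0.17 ng/ml.
- Extreme bound, the whole change within three days: 142/10 = 14.2 ng/ml on that mean.

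For comparison, the standard error of a group mean is 115/√10 = 36.4 ng/ml. Excluding one late sample raises it to 115/√9 = 38.3 ng/ml, or 5.4%. Excluding two raises it by √(10/8) − 1 = 11.8%.

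The illustration has limits. The planning values are borrowed from head and neck cancer. The protocol's baseline is sample 1, taken before radiation and chemotherapy, so starting the whole fall at Optune/TMZ is a simplification.

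**The case for a change.** The strongest case for a change is that validity of a label matters apart from numerical effect. A sample called pre-treatment should be one, the exposure of late samples would differ between groups 2 and 3, and one sentence would remove the doubt. A written plus side also means nothing on the treatment-start reading if the draw must precede the start, so a coordinator has some textual basis for using it. Unlike sample 1, which has a separate stop before radiation and chemotherapy, sample 2 carries its limit only in the phrase that the tolerance follows.

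It stands that the wording is imprecise, and that a draw taken after treatment has begun should not be analysed as a pre-treatment value. It does not stand that the plan accepts such a draw, since both section 4.3 and section 4.1 place this sample before treatment. Figure 2, to which the sentence refers, may also name the reference time, so an unnamed one cannot be established as a gap in the plan. The return-visit, fasting and morning-collection instructions concern blood and saliva, and say nothing about drawing after treatment start. The efficacy sentence is general: no change from sample 2 to sample 3 is specified as a test.

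**Conclusion.** No change to the plan is needed. The tolerance is loosely placed, and on one reading its plus side conflicts with the words before it, but the intended order is stated and a team drawing the sample before starting treatment complies under either reading. No named comparison depends on sample 2: Aim 1 uses sample 1, Aim 2 compares groups after treatment, and the 87% power is untouched. If a draw were late and CD44 changed gradually, the shift in that sample would be 0.02 to 0.07 SD. Its effect on a mean of 10 would be at most 0.76 ng/ml, against a standard error of 36.4. Only an essentially complete response within three days, for which the protocol gives no support, would bring this to 14.2 ng/ml per late sample.

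This conclusion assumes that draw dates and treatment start dates are both recorded, so that a mistimed sample can be recognised and not described as pre-treatment. It also assumes that the study stays, as section 4.2 describes it, an exploratory pilot. If change from sample 2 to sample 3 became a formal endpoint, the reference time would need to be named.

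### Controls are not aligned with the GBM patients on age or sex and CD44 is compared unadjusted, leaving two potential, avoidable confounders in the primary comparison

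*Protocol*

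**What the plan says.** Section 3 gives the first aim: "To compare the differences of CD44 between the control group and the combined cancer groups at baseline". The Power Calculation section (the second section numbered 4.3) treats this as the primary goal, with "sample sizes of n=10 and n=20 (for the control and the cancer groups, respectively"), "expected means of 327 and 185 (for the cancer and the control groups, respectively"), a common SD of 115 and a stated power of 87%.

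On who the controls are, section 4.1 allows "headache, epilepsy or neurodegenerative disorders such as Alzheimer's disease or Multiple sclerosis or Parkinson's disease". Section 4.2 requires participants in all groups to be over 22 and says of sex: "male and/or female, there is no preference at this time". It also restricts controls to patients whose evaluation needed a spinal tap.

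The recruitment and enrollment plan says that "there are several hundreds of patients with neurological disease" enrolled yearly. Coordinators are to find controls by screening files and then interviewing candidates. No matching, quota or stratification by age or sex appears there or elsewhere in the Protocol.

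On analysis, section 4.4 says: "A two sample t-test will be used to compare the biomarker level between groups". A rank-sum test replaces it if the distributions are not symmetric. No covariate is named.

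**The concern.** Aim 1 compares groups defined by disease, so randomisation cannot balance them. The permitted control diagnoses carry no age restriction. A shared lower age limit does not bring two age distributions together, and an open sex criterion does not bring two sex ratios together. With only 10 controls, their age and sex mix will be whatever the clinics supply.

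If CD44 varies with age or sex, the unadjusted difference mixes that variation with the GBM effect. The bias could go either way: it could create a difference where there is none, or hide part of a real one.

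Who is recruited is a Protocol matter. A later analysis plan could add covariates, but it could not change which 10 controls were enrolled.

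**Working it through.** **Inputs from the Protocol (Power Calculation section):** 10 controls, 20 GBM patients, means 185 and 327 (difference 142 ng/ml), SD 115, "significance level of 0.05". Sidedness is not stated.

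**Inputs assumed, because the Protocol gives neither:** r, the within-group correlation of CD44 with age, from 0.2 to 0.4; g, the age gap between groups in SD units, from 0.5 to 1.

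**1. The stated power.** Standard error = 115 × √(1/10 + 1/20) = 115 × 0.3873 = 44.5. Noncentrality = 142 / 44.5 = 3.19. The noncentral t with 28 df and two-sided 0.05 gives 86.8%, which reproduces the stated 87%. A one-sided test would give 92.9%, so the test is evidently two-sided. The 87% takes the whole 142 ng/ml as due to disease.

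**2. Bias and false-positive rate with no true disease effect.** Bias = r × g × 115. The false-positive rate is the rejection rate of the same two-sided t-test at that bias.

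| r × g | Example | Bias (ng/ml) | Share of 142 | False-positive rate |
|---|---|---|---|---|
| 0.1 | r 0.2, g 0.5 | 11.5 | 8% | 5.7% |
| 0.2 | r 0.2, g 1 | 23.0 | 16% | 7.9% |
| 0.3 | r 0.3, g 1 | 34.5 | 24% | 11.6% |
| 0.4 | r 0.4, g 1 | 46.0 | 32% | 16.9% |

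With a weaker correlation of 0.1 and a gap of up to 1 SD, the rate is at most 5.7%.

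**3. Chance imbalance in sex.** If both groups came from populations that are 50% male, binomial sampling of 10 and 20 gives a 16% probability that the observed proportions differ by 30 percentage points or more. This shows how easily imbalance arises. It says nothing about whether CD44 differs by sex, and no bias has been computed for sex.

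**4. Matching compared with adjusting afterwards.** Frequency matching keeps 10 against 20, so the planned power stays at 86.8%. If age and sex are added to the model instead, df = 26, the residual SD is 115 × √(1 − r²), and an age gap inflates the variance by 1 + (2/9)g². Power for 142 ng/ml is then:

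| r | g = 0.5 | g = 1 |
|---|---|---|
| 0.2 | 86.2% | 80.9% |
| 0.3 | 87.9% | 82.9% |
| 0.4 | 90.3% | 85.7% |

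For the lowest cell, the effective SD is 115 × √0.96 × √1.222 = 124.6, and the noncentrality is 142 / (124.6 × 0.3873) = 2.94. Power falls well below this range only with a wider gap: at g = 2 it is 60.8% for r = 0 and 64.9% for r = 0.3.

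**The case against.** The strongest objection is that no confounding has been shown. The Protocol reports no association of CD44 with age or sex and no expected age or sex distribution for any group. At the low end of the assumed range the false-positive rate hardly moves. This stands: age and sex are potential confounders only.

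A reader might infer that an imbalance could not be repaired once 10 controls are enrolled, or that adjustment with 30 participants is too costly. Step 4 does not support this. Over the assumed ranges adjusted power is 81% to 90% against 86.8% unadjusted, and in some cells adjustment gains power. An analysis plan, which is not at hand, could add such a model, and section 4.4 does not exclude a supporting one.

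A reader might also take the several hundred patients a year as the pool available for matching. The usable pool is smaller. Controls must have needed a spinal tap, have enough leftover CSF, meet the exclusions, consent, and come back for blood and saliva. The Protocol does not say how many remain, so it does not show that close matching would be easy.

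Finally, section 4.2 calls this an exploratory pilot, and its wording on sex is an inclusive eligibility statement rather than a decision against balance. That lowers the weight of the point. It does not remove it, because the Protocol still powers a significance test on this comparison.

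**Conclusion.** The point holds in a limited form. The controls are not aligned with the GBM patients on age, beyond a shared lower limit, or on sex, and the planned test is unadjusted. Both factors are therefore potential confounders of the primary comparison that recruitment could largely avoid.

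Its size rests entirely on the assumed correlation and age gap; over the ranges used, the false-positive rate runs from barely above nominal to roughly three times nominal. The documents do not support saying that confounding is present or that it would be beyond repair. This is a low-severity improvement: it costs little, but the matching has to be decided before the controls are recruited.

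**What to change.** - In the recruitment and enrollment plan, have coordinators frequency-match controls to the enrolled GBM patients on sex and broad age bands, as far as the eligible spinal-tap pool allows. Two or three age bands by sex give 4 to 6 cells for 10 controls; ten-year bands by sex would leave about one control per cell, which is too fine.
- Report age and sex by group beside the CD44 result.
- If a gap remains, add an age- and sex-adjusted analysis in support of the planned test.

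**Cost:** control recruitment may be slightly slower. No procedure and no participant is added. Matching on age and sex does not remove confounding from the controls' own neurological disease, or from the GBM baseline sample being taken after surgery, and the report should say so.
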